## 10.0 ADVERSE EVENTS

From the time the ICF is signed, at each evaluation of a subject enrolled in the trial, the investigator or site staff determines whether any adverse events (AE) have occurred, and determines their relationship to the study devices or procedures. All adverse events, study device malfunctions and other product issues must be recorded in the appropriate eCRF section(s).

All adverse events will be collected until a subject's participation in the trial is considered complete.

In the event of an explant for transplant or recovery, adverse events will be collected until the induction of anesthesia for explant.

In the event the device is turned off in lieu of surgical explant, adverse events will be collected until the time the device is turned off.

In the event of an explant for an exchange for another HeartWare MVAD system, the subject will remain in the study post device exchange and adverse events will be collected throughout the subject's participation in this trial.

In the event of an explant for exchange for a non HeartWare MVAD system, adverse events will be collected until the induction of anesthesia for exchange.

Adverse events may be volunteered spontaneously by the subject, or discovered as a result of general, non-leading questioning. If it is determined that an AE has occurred, the investigator should obtain all the information required to complete the AE page of the eCRF, in accordance with the guidelines that accompany it. The investigator must submit to sponsor (or designee) any USADEs, and SAEs occurring during the study **within 24 hours** after being notified of the event and provides additional information, if required by sponsor.

All AEs must be followed until resolution, until the condition stabilizes, until the event is otherwise explained or is judged by the investigator to be no longer clinically significant, or until the subject is lost to follow-up. The investigator is responsible for ensuring that follow-up includes any supplemental investigations necessary to elucidate as completely as practical the nature and/or causality of the AE. This may include additional laboratory tests or investigations, histopathological examinations, or consultation with other health care professionals.

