## 12.6 Other Secondary Endpoints

Other secondary endpoints will also be assessed at 6, 12, 18 months and 24 months. No formal statistical hypothesis tests will be conducted. Analyses for additional secondary endpoints will involve Kaplan-Meier curves for time to event outcomes, descriptive statistics (n, mean, standard deviation, median, minimum and maximum) for quantitative outcomes, and count and frequency results for categorical outcomes. The additional endpoints include:

- Overall Survival (Time to Death)
- Incidence of major bleeding, per INTERMACS definition
- Incidence of all device failures and device malfunctions per INTERMACS definition
- Incidence of major infection, per INTERMACS definition
- Incidence of neurological dysfunction per INTERMACS definition
- Health Status change, as measured by Kansas City Cardiomyopathy Questionnaire (KCCQ) and EuroQoL EQ-5D-5L
- Functional status change, as measured by NYHA and 6-minute walk
- Frequency and rates of adverse events (AEs) throughout VAD support per INTERMACS Definition
- Length of operative time and initial hospital stay
- Re-hospitalizations(excluding planned procedures)
- Transplantations
- Explants

For the Kaplan-Meier analysis (Secondary Endpoint: Overall Survival), transplants, explants for recovery, exchanges (to a device other than the MVAD Pump) prior to endpoint, and any withdrawal or lost to follow-up will be censored, and death will be the defining event.

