### 7.3 Handling of Dropouts or Missing Data

Patients who are lost to follow-up or who withdraw consent prior to specified relative day will be excluded from both denominator and numerator when computing the simple proportion for the primary endpoint (survival at 6 months) and the first secondary endpoint (survival at 24 months). Patients who are lost to follow-up or who withdraw consent will, however, be eligible for the overall survival analysis.

Transplants, explants for recovery and exchanges (to a device other than the MVAD® Pump) will be eligible for survival analysis with their survival status identified at the time of the

procedure. Death with the MVAD® pump in place is the only event that will be considered a failure.

Patient-years and follow-up time are based on database-driven known time on MVAD® support (including post-exchange time). If a patient is on LVAD support at last known follow-up and a later date of death exists, the date of death must be considered the last follow-up for that patient. The patient is known to be alive and assumed to be on MVAD® support up to the date of death.

If a partial date is reported where the day is missing, then the day will be imputed as the first day of the month unless the month is the same month as the device is implanted then the day will be that of implantation with the month and year remaining the same. If a partial date is reported where the month is missing, then the month will be imputed to January unless the year is the same year as the device is implanted then the month will be that of implantation with the year remaining the same. If a partial date where both the day and month is missing, follow details as stated previously.

Missing data for other parameters will not be imputed for analysis unless defined in Section 6. Censoring for the efficacy endpoints is discussed in Sections 6.4.3.1. Missing adverse event dates will be imputed using partial date imputation rules as previously described in this Section.

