## 11 APPENDICES

### 11.1 APPENDIX 1: VARIABLE DEFINITIONS

- Body mass index (BMI; kg/m^2) is calculated as: weight (kg) / [height (m)], rounded to one decimal place.
- Body surface area (BSA; m^2) is calculated using Mosteller formula as:  
$$BSA = (H * W / 3600)^{0.5}$$
  
Where W = weight in kg and H= height in cm

- Weight will be displayed in kilograms (kg), height will be displayed in centimeters (cm), and temperature will be displayed in Celsius (C).
- Weights, heights, or temperatures recorded in alternate units will be converted to the units being displayed using standard conversion formulas.
- Length of Operative Time (mins) = time of chest closure –time of chest incision
- Length of Initial Hospital Stay (Days) = Date of discharge following device implantation – date of implant + 1
- For days on or after the device is implanted:  
Relative Study Day (Rel Day) = Date of Assessment – Date of implant + 1.

For days before the device is implanted:

Relative Study Day (Rel Day) = Date of Assessment – Date of implant.

- Days survived = Date of death/date of event for censoring – Date of implant + 1
  - Days of hospitalization = Date of discharge from hospital – Date of admission + 1
  - Cumulative days of hospitalization after initial hospitalization is the sum of the length of hospital stays after initial hospitalization.
  - Days to explant = Date of explant – Date of initial implant + 1
  - Days to transplant = Date of transplant – Date of initial implant + 1
  - Change from baseline (CFB) = Visit value – Screening/Pre-Implant value
- Calculation of adverse event rate per patient-year**
1. Calculate the patient-years contributed by each patient. The time in the study starts at enrollment. The end date would be the last follow up date (end of study), unless the patient has an explant (when the pump is removed, turned off, or exchanged), dies, or is lost to follow-up prior to the end of study. The patient years are calculated as (date of explant or death or last follow up or end of study – date of enrollment + 1)/365.24. When the number of days is negative, the value will be missing for the patient-years.
  2. Sum the patient-years across all patients in the study. Round to 2 decimal places. This is the denominator.

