## 11.4 APPENDIX 4: STATISTICAL ANALYSIS AND PROGRAMMING DETAILS

Exact binomial confidence intervals:

- *Make sure the outcome variable is coded properly since BINOMIAL option computes the binomial proportion and confidence limits for the first level of the variable. For example, if outcome is coded 'alive vs dead' the output will have test statistics and confidence limits for survival. If the outcome is coded 'death vs survival', then output will have test statistics and confidence limits for the mortality.*
- *Make sure appropriate alpha is specified since the procedure always produces 2sided confidence limits.*
  - *To obtain 1-sided 95% confidence limits, specify alpha=0.10*
  - *To obtain 2-sided 95% confidence limits, specify alpha=0.05*

*The following is example syntax of SAS code to produce the 2-sided 90% exact binomial confidence intervals.*

```
PROC FREQ DATA=sur6;
  WEIGHT n;
  TABLE outcome / BINOMIAL ALPHA=0.10;
  EXACT BINOMIAL;
  OUTPUT OUT out=bio BIN;
Run;
```

*Where n is total number of patients with outcome of alive and total number of patients with outcome of dead at 6 months. Outcome = Alive or Dead*

*For hypothesis of primary endpoint,*

```
Data result; Set
  bio;
  If round(XL_BIN, 0.01) > 0.70 then NI='Pass'; else NI='Fail';
Run;
```

*For hypothesis of secondary endpoint,*

```
Data result; Set
  bio;
  If round(XL_BIN, 0.01) > 0.52.5 then NI='Pass'; else
NI='Fail';
Run;
```

Kaplan-Meier (KM) Survival Analysis:

*The SAS procedure LIFETEST will be used for Kaplan-Meier survival analysis.*

- *Censored = 1 for all patients survived, patients with transplant or explant, patients discontinued without event of death or lost to follow-up*
- *Censored = 0 for all patients died.*

*The following code will be used:*

```
ods listing close;  
ods output CensoredSummary=censor quartiles = _qt;  
PROC LIFETEST DATA = surv TIMELIM=n;  
TIME surdays*censored(1); run; ods  
listing; ods output close;
```

- *Option TIMELIM is the maximum observation period*
- *surdays= number of days survived post implant*
- *dataset censor contains number of patients censored for this analysis*
- *data \_qt contains KM 25% quartile, median, and 75% quartile estimates of time to death*

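### The Kaplan-Meier coding in SAP Appendix 4 conflicts with the censoring rule in SAP 6.4.3.1 and protocol 12.6, and gives some deaths two contradictory codes

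*SAP*

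**What the plan says.** **The rule in the body of the plan.** SAP 6.4.3.1 measures time from implant to death on device. It censors at transplant, explant for recovery, exchange to a device other than the MVAD Pump, withdrawal or loss to follow-up, and otherwise at last contact alive. Protocol 12.6 gives the same list of procedures for the Kaplan-Meier analysis, "transplants, explants for recovery, exchanges (to a device other than the MVAD Pump) prior to endpoint", together with withdrawal and loss. SAP 7.3 counts time after an exchange as MVAD support, says that death with the MVAD "pump in place is the only event that will be considered a failure", and refers to 6.4.3.1 for censoring.

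**The rule in the programming appendix.** SAP Appendix 4 codes "Censored = 1 for all patients survived, patients with transplant or explant", and adds subjects who discontinue alive or are lost. The following bullet codes "Censored = 0 for all patients died". No order of precedence is given.

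**What explant means.** Protocol 10.0 says: "In the event of an explant for an exchange for another HeartWare MVAD system, the subject will remain in the study post device exchange". Protocol 9.4.9 lists pump exchange among the reasons for explantation. SAP 8.8.4.8 allows a patient several explants and tabulates replacement MVAD devices under that heading.

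**Current status.** SAP 5.2, in version 2.0, reports an early stop with fewer than 15 subjects enrolled and replaces summary statistics with case studies. SAP 8.7.3.1 and Appendix 4 still specify the Kaplan-Meier analysis.

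**The concern.** The body of the SAP limits both explant (to recovery) and exchange (to a non-MVAD device). Appendix 4 drops both limits, and it is the text from which a programmer would take the censoring variable. A subject who moves to a second MVAD stays in the study and remains at risk of the event that 6.4.3.1 defines. If that subject is censored at the exchange, a later on-device death disappears from the curve while still counting as a failure in the landmark proportion.

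The opposite error is also open. Protocol 9.4.10 and SAP Table 2 collect survival status up to 12 months after explant, so deaths after transplant or recovery explant can be in the database. A programmer who follows the second bullet literally would count them as events, although 6.4.3.1 censors those subjects at the procedure.

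**Working it through.** **1. The rules side by side.**

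| Subject who dies | SAP 6.4.3.1, protocol 12.6 | Appendix 4 if the first bullet prevails | Appendix 4 if the second bullet prevails |
|---|---|---|---|
| On a replacement MVAD | Event | Censored | Event |
| After transplant | Censored at procedure | Censored | Event |
| After explant for recovery | Censored at procedure | Censored | Event |
| After exchange to a non-MVAD device | Censored at procedure | Censored | Event |

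The first bullet gets row 1 wrong. The second gets rows 2 to 4 wrong. No single ordering of the two bullets reproduces 6.4.3.1.

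**2. The plan's own figures.** The documents state no figure for the time-to-death analysis. The sample size of 57 belongs to the two survival proportions and reproduces: exact power is 86.2% at 6 months (at least 46 of 57 alive) and 83.7% at 24 months (at least 37 of 57). Neither calculation uses the Appendix 4 censoring variable. The natural anchor for the curve is the planned 24-month survival of 70%. With 60 subjects that is 18 deaths, and with no other censoring the product-limit estimate is 42/60 = 70.0%.

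**3. Upward error: k on-device deaths censored just before death.** Assumptions: 60 subjects, 18 deaths at distinct times, no other censoring.

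- If they are the k earliest deaths, 60 − k subjects are at risk and 18 − k deaths follow, so S = 42/(60 − k).
- If they are the k latest deaths, 18 − k deaths occur among 60, so S = (42 + k)/60.

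| k | Lower: 42/(60 − k) | Upper: (42 + k)/60 |
|---|---|---|
| 1 | 42/59 = 71.2% | 43/60 = 71.7% |
| 2 | 42/58 = 72.4% | 44/60 = 73.3% |
| 3 | 42/57 = 73.7% | 45/60 = 75.0% |

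For k = 1 the rise is 1.2 to 1.7 points. Censoring at an exchange halfway to death gives similar values. For example, take the 10th death, with the exchange after 5 deaths: S = (55/60) × (42/54) = 71.3%. The same scheme gives 72.6% for k = 2 and 74.0% for k = 3.

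**4. Downward error: one off-device death coded as an event.** Add to the 18 on-device deaths one subject who is transplanted and dies within 24 months. Censored correctly, S lies between 41/59 = 69.5% (transplant before any death) and 42/60 = 70.0% (transplant after the last on-device death). Coded as an event, S = 41/60 = 68.3%. The drop is 1.2 to 1.7 points.

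**5. At the enrolled size.** Take 14 subjects, the most that fewer than 15 allows, and assume 4 deaths. Then S = 10/14 = 71.4%. One on-device death wrongly censored gives 10/13 = 76.9% to 11/14 = 78.6%.

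**The case against.** The best defence is that SAP 7.3 already says where censoring is defined, namely 6.4.3.1, so the Appendix 4 bullet is shorthand and a careful programmer would follow the body text. That carries weight: the plan does contain the right rule, and no passage says that Appendix 4 overrides it. But the appendix gives explicit codes that contradict the rule, and a reader should not have to guess which text to follow.

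The defence is also right against several stronger readings.

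- *That deaths after an MVAD exchange are removed from the analysis.* The second bullet codes all deaths as events, so the documents show only that such deaths can be removed.
- *That the curve is biased upward.* The same overlap can push it down, as shown for deaths after transplant. The documents also give no evidence that exchanged subjects are at higher risk.
- *That Appendix 1 defines explant to include switch-off.* The words "unless the patient has an explant (when the pump is removed, turned off, or exchanged), dies, or is lost to follow-up" belong to the adverse-event-rate calculation, where they end exposure time. Protocol 10.0 and SAP 6.6.2 treat switch-off as an alternative to surgical explant, so Appendix 4 does not call for censoring at switch-off unless that parenthesis is imported. The real gap is different: 6.4.3.1 speaks of death on device and 7.3 of death with the pump in place, and these need not agree once a pump is off but not removed.

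Finally, SAP 5.2 drops summary statistics, so the curve may never be produced. That limits the consequence. It does not remove the conflict, because 8.7.3.1 and Appendix 4 remain and SAP 7.1 still requires listings of derived variables.

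**Conclusion.** The point holds as a conflict between two stated rules. Appendix 4 contradicts SAP 6.4.3.1, SAP 7.3 and protocol 12.6 on which deaths count, and it assigns both codes to a subject who is explanted and later dies. The error can run in either direction. Under the planning assumptions (60 subjects, 18 deaths, no other censoring) each single miscoded death moves 24-month Kaplan-Meier survival by about 1.2 to 1.7 points. How many deaths would be affected is unknown and is assumed here.

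The reach is small. Time to death is descriptive and carries no hypothesis test, the two performance-goal comparisons do not use this coding, and version 2.0 of the SAP no longer plans summaries. The correction is still worth making because the two texts cannot both be followed.

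**What to change.** Replace the two Appendix 4 bullets with the 6.4.3.1 list and an order of precedence. Each subject's outcome is whichever comes first:

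- death on any MVAD pump, original or replacement: event, timed from first implant;
- transplant, explant for recovery, exchange to a non-MVAD device, withdrawal, loss to follow-up, or last contact alive: censored at that date.

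An MVAD-to-MVAD exchange then neither censors the subject nor restarts the clock.

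Separately, reconcile the wording of 6.4.3.1 (death on device) with 7.3 (pump in place), so that the analysis status of a death after the pump is turned off but not removed is stated once and used throughout.

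The cost is SAP wording and a short change to the derivation code. No new data are needed: the reason for explant is recorded under protocol 9.4.9, survival after explant under 9.4.10, and death details under 9.5.
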